7.2 Treatments to be administered

7.2.1 Titration Period

The study will begin with a Titration Period of up to 3 weeks (at maximum) with the aim of achieving the individually optimized dosage (with a maximum dose of 3mg/24h).

Subjects will be treated at Visit 1 using the following dose titration schedule until their optimal dose is reached ([Table 7-2](#)).

Table 7-2: Dose titration schedule until optimal dose is reached

Visit/Day	Dose
Visit 2/Day 1	1mg/24h
Visit 3/Day 8	2mg/24h
Visit 4/Day 15	3mg/24h

During the Titration Period, the investigator should determine whether the subject has reached his/her optimal dose prior to completing the scheduled assessments for that visit. Subjects who have reached their optimal dose should continue at that dose and remain in the Titration Period until they have reached Visit 5 and enter the Maintenance Period. Subjects are allowed to be up-titrated and down-titrated at the discretion of the investigator during the Maintenance Period.

The optimal dose for each subject will be defined as absence of or maximal reduction in RLS symptoms without intolerable side effects. If the investigator judges that the subject is likely to benefit from a dose increase, then dose titration should continue. If the investigator judges that the subject is unlikely to benefit from a dose increase, then the dose is defined as optimal.

If AEs occur during the Titration Period that are thought to be the result of excessive dopaminergic stimulation (eg, intolerable nausea/vomiting), subjects should be down-titrated to their previous dose level and continue at that dose until they reach Visit 5 and enter the Maintenance Period.

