13.4 Planned safety and other analyses

13.4.1 Safety analyses

All safety data will be analyzed for the SS. In general, Baseline is defined as the last assessment before first dosing in the previous study of rotigotine, SP1006.

Safety variables will be analyzed in a descriptive way. Results will be presented overall.

Individual listings of AEs (age, body height, body weight, race, gender, system organ class [SOC]), and preferred term according to the Medical Dictionary for Regulatory Activities [MedDRA®], AE as reported, start and end with relative days to study medication administration, duration, intensity, seriousness, and relationship to study medication, action taken and final outcome) will be provided. The start and stop of each AE will be given as absolute and relative to the time of patch application. In addition, listings for subjects with SAEs, AEs leading to discontinuation, and other significant AEs will be provided.

The incidence of treatment-emergent AEs will be summarized in frequency tables by actual dose at the start of the event, modal dose, and intensity, ordered by primary SOC, high level term, and PTs. The incidence of drug-related AEs will be described in the same way. Frequency tables for withdrawals due to AEs by last dose and by modal dose will be provided.

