3 DATA ANALYSIS CONSIDERATIONS

3.1 General presentation of summaries and analyses

Statistical analysis and generation of tables, figures, subject data listings, and statistical output will be performed using SAS Version 9.3 or higher. All tables and listings will use Courier New font size 9.

A complete set of raw data listings containing both all documented data and all calculated data (eg, changes from Baseline) will be generated.

Unless otherwise noted, all summaries will be displayed by the final dose group (rotigotine 1mg/24h, rotigotine 2mg/24h and rotigotine 3mg/24h). The ‘final dose’ is the final titrated or back-titrated dose level administered at the start of the Maintenance Period. The ‘final dose’ for subjects who withdrew before the Maintenance Period is defined as the last dose taken. A summary with all dose groups combined (i.e., total column) will be presented for the demographic and Baseline characteristics, and for the prior and concomitant medications.

In general, summary statistics for quantitative variables will include n (number of available measurements), arithmetic mean, SD, median, minimum, and maximum. For categorical parameters, descriptive statistics will consist of the number and percentage of subjects in each category. Unless otherwise specified the denominator for calculating percentages will be the number of subjects in the respective population.

Unless otherwise noted, all percentages with the exception of 0 and 100 will be expressed to 1 decimal place. 100% will be presented as integer. If a category has the frequency 0 the percentage value will be omitted. Mean and median changes from baseline lower than the minimal displayable change will be displayed without sign (e.g., -0.00 will be displayed as 0.00).

For descriptive statistics, the following rules regarding decimal places will apply:

- n will be an integer.
- Mean, SD, and median will use 1 additional decimal place compared to the original data.
- Minimum and maximum will have the same number of decimal places as the original value.

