3.2.3 Visit mapping

The visits are planned for the follow days:

Visit	Day	Visit Window
Visit 1 (Screening)	Day -4 to Day -1	
Visit 2, Day 1	Day 1	
Visit 3, Day 8	Day 8	± 3 Days
Visit 4, Day 15	Day 15	± 3 Days
Visit 5 (SoM)	Day 22 (or after reaching optimal dose)	± 3 Days
Visit 6 (Month 3)	90 Day after SoM	± 14 Days
Visit 7 (Month 6)	180 Day after SoM	± 14 Days
Visit 8 (Month 9)	270 Day after SoM	± 14 Days
Visit 9 (EoM)	360 Day after SoM	± 14 Days
Safety Follow-Up	30 Days after End of Taper Period	± 5 Days

During the Titration Period, the investigator should determine whether the subject has reached his/her final titrated dose level prior to completing the scheduled assessments for that visit. Subjects who have reached their final dose level should proceed to the Maintenance Period (Visit 5) and complete those assessments. Subjects who are back-titrated during the Titration Period will automatically enter the Maintenance Period.

Analysis by visit will be done as documented in the eCRF, i.e., no visit correction will be conducted due to deviations from scheduled time points.

Assessments at premature Withdrawal of the study are documented in the eCRF pages of Visit 9 (EoM/ Withdrawal). For data listings, assessments of Withdrawal Visit and of Visit 9 as scheduled will be presented separately as

- Premature Withdrawal for subjects who prematurely terminated the study
- Visit 9 (EoM) for subjects who completed the study.

Unscheduled assessments may be recorded during the study. Information collected in the log forms (e.g., AEs and concomitant medications) is included in the analysis. However, assessments at unscheduled visits will not be considered in the by visit analysis unless data captured at these visits falls within the SAP defined visit windows shown above and there was no corresponding endpoint data collected at the same scheduled visit. The information collected during unscheduled visits will be presented in the listings as an unscheduled visit.

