10 SAFETY ANALYSES

All safety analyses will be conducted for the SS and results will be presented by final dose group and for all subjects combined.

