10.1 Extent of exposure

The duration of exposure will be calculated as (date of last patch removal – date of first patch application + 1 day).

The final dose level ('final dose') is defined as the dose administered at the start of the Maintenance Period (i.e., at Visit 5) and intended to be used during the Maintenance Period. If the subject down titrates to the previous dose during the Titration Period and continues on that dose at Visit 5, then the back-titrated dose level is the 'final dose'.

The determination of the dose of longest duration is based on the entries given in the drug dosing log of the eCRF. The duration of a single dose will be calculated as the sum of the durations of each dosing interval with intake of the respective dose whereas the duration of each dosing interval will be calculated as (end date – start date).

Where more than one dose has the same longest duration, the highest dose will be selected. For subjects who dropped out during the Titration Period, the last applied dose during the Titration Period will be used as dose of longest duration.

A listing will be presented for the following variables:

- Duration of exposure (days)
- Final dose level (mg/24h) at the start of Maintenance (1mg/24h, 2mg/24h and 3mg/24h)
- Dose of longest duration (1mg/24h, 2mg/24h and 3mg/24h)

A listing of patch adhesiveness findings, including date and time of detachment, location and side of body, percent adherence and kit number will be provided.

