10.2 Adverse events

Adverse events will be documented throughout the entire study on an ongoing basis. TEAEs are defined as events that started during the Treatment Period or within 30 days following the end of the Treatment Period (i.e., on or after the date of first patch application and within 30 days following the date of last patch removal) or any unresolved event already present before administration of treatment that worsens in intensity following exposure to the treatment. For AEs with a partial or missing start date, the imputation rules as described in [Section 4.2.2](#) will be applied.

Adverse events with a missing start date are defined as treatment-emergent if the end date of the AE is not on or before the date of first patch application.

An AE with action taken regarding study medication reported on the AE page of the eCRF as “drug permanently withdrawn” will be regarded as an AE leading to discontinuation of study medication.

Adverse events which have the question “Serious Adverse Event?” answered “yes” are considered serious.

Treatment emergent AEs will be tabulated by MedDRA SOC, High Level Term (HLT) and PT. The number and percentage of subjects experiencing each event at least once will be summarized in addition to the number of events. In summaries of TEAEs by relationship and intensity, respectively, the number of events will not be presented.

All summaries will be sorted alphabetically by SOC and HLT and by frequency of events (PT) within HLTs. If there is more than one PT with the same frequency these events will be sorted alphabetically.

An overview of the incidence and frequency of all TEAEs, serious TEAEs, TEAEs leading to discontinuation of study medication, related TEAEs, severe TEAEs, all deaths, and TEAEs leading to death will also be provided.

The following tabular summaries will be presented also.

- TEAEs
- TEAEs by intensity
- TEAEs by maximum intensity
- TEAEs by relationship to study medication per the Investigator
- Serious TEAEs
- Serious TEAEs by Relationship to study medication per the Investigator
- non-serious TEAEs above reporting frequency threshold of 5%

Individual subject data listings will be presented for all AEs.

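### TEAE tables are split by the Visit 5 dose, so an event that forces a step-down in titration is counted under a lower dose than the one it began on

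*SAP*

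**What the plan says.** SAP section 10 states that safety "results will be presented by final dose group and for all subjects combined". Section 10.1 ties final dose to the start of Maintenance at Visit 5 and covers step-downs explicitly: "If the subject down titrates to the previous dose during the Titration Period and continues on that dose at Visit 5", the lower level is the final dose. For early dropouts, SAP section 3.1 says that the final dose "for subjects who withdrew before the Maintenance Period is defined as the last dose taken".

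Protocol section 7.2.1 links adverse events to dose. When an event in titration is attributed to excessive dopaminergic stimulation, "subjects should be down-titrated to their previous dose level and continue at that dose until they reach Visit 5". SAP section 3.2.3 describes the timing differently ("Subjects who are back-titrated during the Titration Period will automatically enter the Maintenance Period"). The two texts need reconciling, but either way the lower dose becomes the final dose.

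Protocol section 13.4.1 planned other groupings: "The incidence of treatment-emergent AEs will be summarized in frequency tables by actual dose at the start of the event, modal dose, and intensity". Drug-related events were to be shown the same way, and "Frequency tables for withdrawals due to AEs by last dose and by modal dose will be provided". In SAP section 10.2, "Treatment emergent AEs will be tabulated by MedDRA SOC, High Level Term (HLT) and PT", followed by an overview and tables by intensity, relationship, seriousness and frequency. None uses dose at onset, modal dose or last dose. SAP section 3.6 still promises some summaries by longest or actual dose but names none. Section 3.9 says in general terms that protocol analyses are cut because the study stopped early.

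**The concern.** The column in which a subject appears is partly decided by the adverse event itself. A subject who cannot tolerate 3 mg/24h and steps down to 2 mg/24h takes that event into the 2 mg/24h column, and the 3 mg/24h column keeps those who tolerated it. This is systematic misplacement, not noise.

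Other errors run the opposite way or in no fixed direction. Early events on 1 or 2 mg/24h in subjects who go on to 3 mg/24h are counted under 3 mg/24h. Events after a dose change in Maintenance stay with the Visit 5 dose.

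The by-dose columns could therefore flatten or reverse the true dose pattern. A reader of the study report could easily take them as a statement about tolerability by dose in adolescents, which they cannot be.

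**Working it through.** The plan has no figure to reproduce here. The direction follows from the rules; the size needs assumed inputs.

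**Simple count (assumed).** Of 138 subjects (the planned maximum), suppose 92 reach 3 mg/24h and 46 settle at 2 mg/24h. Suppose 20% of the 92 (18 subjects) have an event on 3 mg/24h and step down, and nobody else has an event.
- By onset dose: 3 mg/24h 18/92 = 19.6%, 2 mg/24h 0/138.
- By final dose: 3 mg/24h 0/74, 2 mg/24h 18/(46+18) = 18/64 = 28.1%.

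**Fuller model (assumed).** Weekly risks of an intolerable event are 5/10/20% at 1/2/3 mg/24h, and 20/30/50% of subjects need 1/2/3 mg/24h. After an event, a share w withdraws and is grouped by last dose taken (read as the titration dose, not a taper dose). The rest step down one level, or stay at 1 mg/24h, and do not escalate again. As fractions of all subjects:
- Events by onset dose: E1 = 0.20×(1−0.95³) + 0.80×0.05 = 0.0685; E2 = 0.30×0.95×(0.10+0.90×0.10) + 0.50×0.95×0.10 = 0.1017; E3 = 0.50×0.95×0.90×0.20 = 0.0855. The sum is 0.2557, so the all-subjects figure is 25.6% under either grouping.
- Ever exposed: 1; 0.80×0.95 = 0.76; 0.50×0.95×0.90 = 0.4275.
- No event, by Visit 5 dose: F1 = 0.20×0.95³ = 0.1715; F2 = 0.30×0.95×0.90² = 0.2309; F3 = 0.50×0.95×0.90×0.80 = 0.3420.

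By onset dose: 0.0685/1 = 7%; 0.1017/0.76 = 13%; 0.0855/0.4275 = 20%.

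By final dose, the columns hold E1+(1−w)E2, wE2+(1−w)E3 and wE3 events; each denominator adds F1, F2 or F3. With w = 0: 0.1702/0.3417 = 50%; 0.0855/0.3164 = 27%; 0/0.3420 = 0%. The share counted under a dose other than the onset dose is (1−w)(E2+E3)/(E1+E2+E3) = (1−w)×0.1872/0.2557.

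| Share withdrawing at the event | Final-dose columns, 1/2/3 mg/24h | Events under another dose |
|---|---|---|
| 0% | 50/27/0% | 73% |
| 25% | 46/28/6% | 55% |
| 50% | 41/29/11% | 37% |
| 100% | 29/31/20% | 0% |

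With weekly risks of 2/4/8% and no withdrawals, the columns read 27/12/0% by final dose against 3/5/8% by onset dose.

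**Any TEAE.** Add one Maintenance risk m at the Visit 5 dose for subjects still in the study. Each column becomes (titration events + m×F)/(titration events + F). With m = 30/40/50% and no withdrawals, the 1 mg/24h column is (0.1702+0.3×0.1715)/0.3417 = 65%.

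| Weekly titration risks | Maintenance risks | Withdrawing | Final-dose columns |
|---|---|---|---|
| 5/10/20% | 30/40/50% | 0% | 65/56/50% |
| 5/10/20% | 30/40/50% | 50% | 59/57/56% |
| 5/10/20% | 50/60/70% | 0% | 75/71/70% |
| 5/10/20% | 50/60/70% | 50% | 71/72/73% |
| 2/4/8% | 50/60/70% | 0% | 64/65/70% |

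A true 20-point rise in Maintenance risk looks falling, flat or, in the mildest case, like a gap of 70−64 = 6 points. Dose changes in Maintenance were not modelled.

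**The case against.** The SAP is open about the cut. Its introduction says that the analysis is much more limited than the protocol's, section 3.9 says that protocol analyses will not be performed as defined, and the amendment rationale says that tables were reduced. The primary variables, occurrence of TEAEs and TEAEs leading to permanent withdrawal, are not defined by dose. There is no dose-response objective, no randomisation to dose and no testing. Protocol section 13.4.1 itself says that results are presented overall, and that column survives. All adverse events are listed with relative days, so dose at onset could probably be rebuilt subject by subject. All of this stands and limits the weight of the point. It does not explain why by-dose columns were kept under the one grouping that the step-down rule distorts, and no listing is said to show dose at onset.

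The illustration also rests on invented risks. The 0% at 3 mg/24h holds by construction, because every modelled event there forces a step-down or withdrawal and nobody withdraws in that row. Only events attributed to dopaminergic excess trigger the rule, and subjects have already tolerated at least one dose step in SP1006, so the assumed risks may be high. That is fair: the direction is certain, the size is not.

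The strongest point concerns the remedy. Everyone starts at 1 mg/24h, so crude onset-dose incidence has its own exposure bias. With Maintenance risks of 50/60/70%, titration risks of 5/10/20% and no withdrawals, it reads:
- 1 mg/24h: 0.0685+0.5×(0.1017+0.1715) = 21%
- 2 mg/24h: (0.1017+0.6×0.3164)/0.76 = 38%
- 3 mg/24h: (0.0855+0.7×0.3420)/0.4275 = 76%

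A 20-point gradient becomes 76−21 = 55. Onset-dose tables therefore need days at dose beside them.

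**Conclusion.** The point holds and should be fixed. Followed exactly, the SAP counts titration events that cause a step-down under a dose on which they did not begin, and no table keeps the protocol's onset-dose, modal-dose or last-dose groupings. Under the assumptions above, between none and about three quarters of intolerable titration events are misplaced, depending on how many affected subjects withdraw. For any TEAE the effect runs from a reversed order to a compressed gap. Overall incidence and the primary variables are not biased, and subjects who withdraw in titration are largely placed correctly. The harm is confined to how the by-dose columns would be read.

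**What to change.** - **SAP 10.2:** restore the protocol's tables of TEAEs and related TEAEs by actual dose at onset, and of TEAEs leading to discontinuation by last dose. Use subjects ever exposed to that dose as denominator and show days at that dose; both are additions to the protocol text. Footnote that a subject can appear in more than one column. State how events starting in the Taper Period or after last patch removal are assigned.
- **SAP 10:** keep the all-subjects column as the main display. If final-dose columns stay, footnote that they do not show dose at onset and carry no dose-response meaning.
- **SAP 3.6:** name the summaries that use actual or longest dose.
- **SAP 3.9:** say whether the modal-dose tables are dropped or replaced by the dose of longest duration already derived in section 10.1.

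If numbers prove too small for onset-dose tables, the minimum is the footnote, the wording in 3.6 and 3.9, and dose at onset as a column in the adverse event listing.

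The cost is SAP wording and a little programming from the existing drug dosing log and event dates. No new data are needed. Columns will overlap and may be small after early termination.

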10.1 Extent of exposure

The duration of exposure will be calculated as (date of last patch removal – date of first patch application + 1 day).

The final dose level ('final dose') is defined as the dose administered at the start of the Maintenance Period (i.e., at Visit 5) and intended to be used during the Maintenance Period. If the subject down titrates to the previous dose during the Titration Period and continues on that dose at Visit 5, then the back-titrated dose level is the 'final dose'.

The determination of the dose of longest duration is based on the entries given in the drug dosing log of the eCRF. The duration of a single dose will be calculated as the sum of the durations of each dosing interval with intake of the respective dose whereas the duration of each dosing interval will be calculated as (end date – start date).

Where more than one dose has the same longest duration, the highest dose will be selected. For subjects who dropped out during the Titration Period, the last applied dose during the Titration Period will be used as dose of longest duration.

A listing will be presented for the following variables:

- Duration of exposure (days)
- Final dose level (mg/24h) at the start of Maintenance (1mg/24h, 2mg/24h and 3mg/24h)
- Dose of longest duration (1mg/24h, 2mg/24h and 3mg/24h)

A listing of patch adhesiveness findings, including date and time of detachment, location and side of body, percent adherence and kit number will be provided.

10.2 Adverse events

Adverse events will be documented throughout the entire study on an ongoing basis. TEAEs are defined as events that started during the Treatment Period or within 30 days following the end of the Treatment Period (i.e., on or after the date of first patch application and within 30 days following the date of last patch removal) or any unresolved event already present before administration of treatment that worsens in intensity following exposure to the treatment. For AEs with a partial or missing start date, the imputation rules as described in [Section 4.2.2](#) will be applied.

Adverse events with a missing start date are defined as treatment-emergent if the end date of the AE is not on or before the date of first patch application.

An AE with action taken regarding study medication reported on the AE page of the eCRF as “drug permanently withdrawn” will be regarded as an AE leading to discontinuation of study medication.

Adverse events which have the question “Serious Adverse Event?” answered “yes” are considered serious.

Treatment emergent AEs will be tabulated by MedDRA SOC, High Level Term (HLT) and PT. The number and percentage of subjects experiencing each event at least once will be summarized in addition to the number of events. In summaries of TEAEs by relationship and intensity, respectively, the number of events will not be presented.

All summaries will be sorted alphabetically by SOC and HLT and by frequency of events (PT) within HLTs. If there is more than one PT with the same frequency these events will be sorted alphabetically.

An overview of the incidence and frequency of all TEAEs, serious TEAEs, TEAEs leading to discontinuation of study medication, related TEAEs, severe TEAEs, all deaths, and TEAEs leading to death will also be provided.

The following tabular summaries will be presented also.

- TEAEs
- TEAEs by intensity
- TEAEs by maximum intensity
- TEAEs by relationship to study medication per the Investigator
- Serious TEAEs
- Serious TEAEs by Relationship to study medication per the Investigator
- non-serious TEAEs above reporting frequency threshold of 5%

Individual subject data listings will be presented for all AEs.

10.3 Clinical laboratory evaluations

The following laboratory parameters are measured within the study:

- Hematology parameters: Hematocrit (HCT), Hemoglobin (HGB), Platelets (PLAT), Red Blood Cells (RBC), White Blood Cells (WBC), and differential count and percentile (Lymphocytes, Basophils, Eosinophils, Monocytes, Neutrophils)
- Liver Function Tests and other Chemistry parameters: Alanine Aminotransferase (ALT), Aspartate Transaminase (AST), Albumin, Alkaline Phosphatase (ALP), Bicarbonate (Total CO₂), Blood Urea Nitrogen (BUN), Calcium, Chloride (CL) Creatinine, Ferritin, Gamma-glutamyl transferase (GGT), Glucose, Iron Binding Capacity Total (IBCT), Iron Binding Capacity Unsaturated (IBCU), Lactate Dehydrogenase (LDH), Potassium, Phosphorus, Serum Iron, Sodium, Total cholesterol, Total bilirubin, Total protein, Transferrin, Uric acid
- Endocrine parameters: Estradiol (females only), Follicle-stimulating Hormone (FSH), Insulin-like Growth Factor 1 (IGF-1), Luteinizing Hormone (LH), Progesterone (females)

only), Prolactin, Testosterone (males only), Thyroxine Free (T4FR), Triiodothyronine (T3), Thyroid Stimulating Hormone (TSH)

- Endocrine normal ranges are provided by the central lab and included in the dataset specifications.
- Urinalysis: Color, Appearance, Glucose, Protein, Blood, Ketones, Urine Pregnancy Test

Summary statistics of the observed values and their change from Baseline and the frequency of abnormal values based on normal ranges will be presented by visit for laboratory parameters of hematology, chemistry and endocrinology.

Laboratory data outside the reference range will be highlighted with “L” for low and “H” for high in all laboratory subject data listings where applicable.

Individual subject data listings will be presented for laboratory parameters of hematology, chemistry and endocrinology. Urinalysis and pregnancy test results will only be listed.

